4.0 Research participants

4.1 Study Population

We plan to enroll up to 200 caregiver and their infant while the pair is in the mother-baby unit at KATH. The following criteria outline inclusion and exclusion criteria for being in the study.

Based on numbers from KATH, in 2013 there were 567 infants born with birth weights below 1800 grams (gestational age is not available) who live at least 28 days. Given most term infants are greater than 1800 grams at birth, we presume this is our recruitment pool. Based on these numbers, we estimate we will need to recruit 26% (150/567) of the clinical population over the course of a year.

4.2 Study Eligibility: Inclusion and Exclusion Criteria Inclusion

In order to be eligible to participate in this study, the caregiver-infant pair must meet all of the following. The information in [brackets] specifies where this information will typically be ascertained. A caregiver is the person primarily responsible for feeding the infant. This is typically the mother. In cases where the mother is unwell or deceased, we may enroll a caregiver who is a biological family member designated as the person primarily responsible for feeding the infant. Relations who meet this criterion include a biological grandmother or aunt of the infant. The admitting doctors will do the scoring using the physical characteristics of the modified Dubowitz assessment tool (see final page of this document). The admitting doctors will be House Officers supervised by Paediatric Residents and will be qualified (BSc Human Biology, MB ChB – which is analogous to MD) and members of the Ghana College or the West Africa College of Physicians.

Inclusion

- Infant
 - Infant was born preterm (<37 weeks gestational age) at time of birth [chart]
 - Infant's corrected gestational age is <37 weeks per the modified Dubowitz score on date of enrollment [chart].
 - Infant diagnosed with feeding difficulties [provider]
 - Infant is a patient in the mother-baby unit at KATH [chart/location]
 - Infant is clinically indicated to start cup feeding (including an infant who has a nasogastric tube and is cup feeding or indicated to start cup feeding) [provider]
 - Infant has an anticipated hospital stay that is at least 48 hours [provider]
- Caregiver:
 - Caregiver must be at least 18 years of age [caregiver]
 - Caregiver must be one of the following biologic family members of the infant [caregiver]:
 - Mother
 - Grandmother
 - Aunt
 - Caregiver must self-identify as the primary feeder of the infant [caregiver]

- Prior experience feeding the potential infant participant with nipple feeding (e.g. breast feeding, bottle feeding, or nasogastric [NG] tube) is okay but is not required [caregiver].
- Caregiver verifies willingness to comply with all study procedures [caregiver]

Exclusion

- Infants with a congenital anomaly except for minor anomalies (e.g. an extra digit or ear tag is okay) [provider]
- Infant has other condition or situation that makes them unlikely to be able to comply with study procedures. Examples include the infant anticipated to not be in hospital long enough, infant has a suspected intestinal obstruction, or necrotizing enterocolitis. [provider]
- Infants without a mother, grandmother, or aunt caregiver [provider or caregiver]
- Infant has been enrolled in another study at KATH that would interfere with his/her ability to participate in this study.

5.0 Study procedures

Study participants will be asked to cup feed their infant with the generic cup and the Nifty Feeding Cup in the randomized order assigned. The caregiver will feed their infant with each cup at least 2 times before we measure feedings with the cup. Mothers will not be asked to exclusively cup feed during this study. Preterm infants started on cup feeding will typically start with a cup and then gradually transition to breastfeeding. Mothers are counseled to attempt breast feeding while their infant is using the feeding cup. Study procedures are aligned with KATH practice so the mother will not do anything different than what is clinically indicated as best for mother and baby.

Since infant participants are inpatients, the term ‘visit’ is meant loosely to indicate the sequential study activities that will take place. Research staff may check-in with the caregiver at any time during the participation in the study to coordinate study activities. The day and time of each study visit is an estimate but each visit will be completed before the next. To ensure the infant is clinically indicated to cup feed, prior to each feed we measure, the research assistant (RA) will consult with a provider to make sure the infant can be cup fed.

The caregiver will feed their infants the type of milk/formula in amounts determined by the clinical provider. The study team will not be involved in providing guidance regarding type of milk or amount recommended other than tracking it.

If the infant and/or caregiver have health, social or other problems that arise in the course of study participation that prevent either of them from participating in study visits, we will discontinue them from the study

Details of the tools (e.g. Surveys) and procedures (e.g. Feeding Assessment) used at each visit are outlined in Section 6 below. Also refer to the **Schematic of Study Procedures** found

immediately after the Protocol Summary and the **Visit Activities Schedule**, an Appendix to the protocol.

We estimate the RAs will each be able to manage a workload of 2-3 participants per week and that based on this rate, it will take about 1 year to complete enrollment and data collection activities.

Study participants will be discharged from hospital when clinically appropriate. Participants will not be retained in hospital to finish the study procedures.

5.1 Visits

5.1.1 Visit 1. Baseline (Day 1, Hour 0)

After the consent process, the RA will conduct the Baseline visit. She will:

- Obtain the random assignment of which cup to introduce first
- Administer the Baseline Survey
- Measure the infant's current weight and length.
- Provide the caregiver with assigned Cup 1 and the instructions for use.

5.1.2 Visit 2. Cup 1 Feed 1 (Day 1, >4 hours after V1)

To allow the caregiver time to feed her infant with Cup 1 for at least two times without being observed by the RA, we will conduct this visit >4 hours after V1. The RA will periodically check in to see if at least two feedings have occurred and then conduct V2. During Visit 2, the RA will:

- Conduct the Feeding Assessment

5.1.3 Visit 3. Cup 1 Feed 2 (Day 1, >2 hours after V2)

The RA will measure a second feeding at V3. There may or may not be feedings between V2 and V3. During Visit 3, the RA will:

- Conduct the Feeding Assessment
- Remove Cup 1 so it is not inadvertently or preferentially used over Cup 2
- Provide the caregiver with Cup 2 and the instructions for use.

5.1.4 Visit 4. Cup 2 Feed 1 (Day 2, >4 hours after V3)

To allow the caregiver time to feed her infant with the Cup 2 for at least two times without being observed by the RA, we will conduct this visit >4 hours after V3. The RA will periodically check in to see if at least two feedings have occurred and then conduct V4. During Visit 4, the RA will:

- Conduct the Feeding Assessment

5.1.5 Visit 5. Cup 2 Feed 2 (Day 2, >2 hours after V4)

This is the last visit while the participant is an inpatient in the hospital. The RA will measure a second feeding at V5. There may or not be feedings in-between V4 and V5. We will provide the thank you at this visit. During Visit 3, the RA will:

- Conduct the Feeding Assessment
- Conduct In-Hospital Preference Survey

Return Cup 1 to the caregiver, Cup 2 will remain with the caregiver after completion of the study procedures.

- Provide thank you
- Schedule Follow-Up Survey

5.1.6 Discharge Data Abstraction

We will schedule the Follow-up Survey at the end of Visit 5 based on anticipated discharge date. We will subsequently abstract actual discharge date and health information from the record (See Section 5.2.5 below). We may reschedule visit 6 if the discharge date is substantially different than anticipated.

5.1.7 Visit 6. Follow-up Survey (Week 4 post-discharge)

During Visit 6 the RA will conduct the Follow-up Survey by telephone or in person for those who return to clinic for their 1 month follow-up and thank the participant verbally one last time for their participation.

5.2 Procedures and Evaluations

5.2.1 Intervention

Random Assignment. Random assignment will be given using sealed numbered sequential envelopes prepared by the PI and stored at KATH. PI [name], who will do the statistical analysis, will not prepare the randomization schedule we will use. PI [name] and colleagues at PATH will prepare the randomization schedule.

Cup. We will provide all cups used for the study. The first cup used as determined by the random assignment is called Cup 1. The other cup is called Cup 2. We will use the Nifty Feeding Cup being produced by Laerdal Global Health. We will use a small generic medicine cup as the comparison.

Instructions for Use. We will show a short video that shows how to use the Nifty Feeding Cup and a short video that shows how to use the generic cup. Videos will be shown to participant on a table or laptop device. If the participant has a video capable phone, the video may be loaded on to their personal device for reference. The video will include instructions on how to use and clean the cups being used. These videos have been provided to the IRB.

5.2.2 Outcomes

Outcomes related to intake, spillage, and duration will be measured at each Feeding Assessment, which will take place at Visit 2 through 5. Caregiver satisfaction will be measured during Feeding Assessment related to the experience of that feed (V2-V5). Caregiver satisfaction will be measured with the In-Hospital Preference Survey (V5) and the Follow-up Survey (V6).

Milk Intake. We will measure amount (in ml) and weight (in grams) of milk in the cup before the feeding. We will measure the amount and weight of milk in the cup after the feeding. If the cup is refilled, we will measure the amount and weight before and after the refill. The amount and weight will be recorded on the Feeding Assessment case report form. We will use a digital scale

to determine all weight measurements. The weight per ml will be estimated based on the baseline measure and used to adjust the gross measure of intake by subtracting out spillage that occurred during the feed. We will calculate intake per feed from these measures less the amount spilled.

Spillage. We will account for spillage of milk by using a baby bib cloth for all feedings. Each caregiver-infant pair will be provided with a bib cloth for each observed feeding. The bib cloth will be weighed before and after each feed and the weights recorded on the Feeding Assessment form. The difference between the pre and post weights will be used as the measure of the amount spilled. A digital scale will be used and milk weight will be in grams. Spillage will be reported as a percent with the amount of milk in grams spilled/mopped up divided by the total amount of milk weighed in grams less the total amount of milk not used.

Caregiver Satisfaction. Our primary measure of caregiver's satisfaction will be the cup she prefers [secondary] and rated satisfaction [primary] which will be recorded in the In-Hospital Preference Survey completed after the caregiver has finished the feeding portion of the study (V5). A secondary measure will be what the caregiver reports uses most of the time measured in the Follow-up Survey 4 weeks post-discharge (V6). We will also measure the caregiver's satisfaction with each cup after each feeding measured in the Feeding Assessment and in the In-Hospital Preference Survey (V2-V5).

Duration of Feed. The RA will measure duration of feeding in minutes and seconds with a digital timer. The timer will begin at the time the cup first touches the infant's lip and stop when the cup last leaves the infant's mouth. If there are stops and starts in the feeding (e.g. mother needs to express more milk), we will also record this information. The time measured will be recorded on the Feeding Assessment form.

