8.0 Study product(s)

The Nifty Feeding Cup by Laerdal will be the version of the NIFTY cup used for this study. The Nifty Cup manufactured by Laerdal Global Health (see:

<http://www.laerdalglobalhealth.com/doc/2576/Nifty-Feeding-Cup#/Info>) is a reusable product for feeding breast milk to newborns with breastfeeding difficulties (Figure 1). It is a simple to use, easy to clean and culturally appropriate feeding solution which allows the infant to control the pace of feeding. Product specifications are as follow:

- Reusable for use by multiple newborns
- Suitable for reprocessing with the following methods:
 - Steam autoclaving at 136 °C, 10-20 minutes
 - Chemical disinfection with 0.5% chlorine solution, 20 minutes, and rinsed 3 times with clean water afterwards
 - Boiling in water, 10 minutes
- Made with silicone rubber
- Safe for food contact according to *USFDA 21 CFR 177.2600 regulation* Mass: Approx. 23.5 g
- Volume: 5 to 40 ml; the cup has tick marks every 5ml and numerals every 10 ml

- Operating Temperature: -18 °C to +50 °C
- Storage temperature: -40 °C to +60 °C
- Not made with natural rubber latex

For every batch of silicone materials used in the Nifty feeding cup by Laerdal, material samples are sent to an independent test lab for testing to USFDA requirements applicable for food contacting rubber materials, 21 CFR 177.2600.

In all geographies, the Nifty Cup is being commercialized by the manufacturer as a cup for general infant feeding and not a medical device. To implement this decision, Laerdal Global Health:

- o Will only label/promote it for general infant feeding—there will be no references to specific health conditions such as cleft palate or other facial abnormalities
- o Will include “not for medication dispensing” in the use instructions and possibly on the cup itself
- o Will comply with all applicable US and European regulations for food contact materials

The proposed study will be conducted in Ghana, in its entirety. As the USFDA does not have jurisdiction in Ghana, the study is not subject to the USFDA regulations. We are consulting with the Ghana FDA to determine the documentation necessary to conduct this study in Ghana. The Ghana FDA has reviewed this protocol.

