The generic cup that will be used in this study is a small medicine cup 30 ml in size (Figure 2). Small medicine cups are manufactured by a variety of manufacturers and are commonly used in health facilities to feed breastmilk to infants who are having breastfeeding difficulties. The cups are generally translucent, calibrated with a variety of measurements including 2.5-30 mL.

Figure 2: Generic medicine cup

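### Milk intake appears to be calculated from millilitre readings in two differently marked cups; defining it from the weights already recorded would remove a possible cup-linked reading error

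*Combined protocol and SAP*

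**What the plan says.** Section 5.2.2 takes two measurements of the milk at each step. Before the feed: "We will measure amount (in ml) and weight (in grams) of milk in the cup before the feeding". Afterwards: "We will measure the amount and weight of milk in the cup after the feeding". For refills: "If the cup is refilled, we will measure the amount and weight before and after the refill". Spillage is the weight gain of a bib, in grams. The text links the two units in this way: "The weight per ml will be estimated based on the baseline measure and used to adjust the gross measure of intake by subtracting out spillage". It closes with "We will calculate intake per feed from these measures less the amount spilled", without saying whether the measures meant are the ml or the gram values.

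The spillage outcome in the same section is wholly gravimetric: "Spillage will be reported as a percent with the amount of milk in grams spilled/mopped up divided by the total amount of milk weighed in" (the sentence goes on to give the unit as grams and to take off unused milk).

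Section 8.0 describes the cups. For the Nifty: "Volume: 5 to 40 ml; the cup has tick marks every 5ml and numerals every 10 ml". Medicine cups are described only in general terms, as "calibrated with a variety of measurements including 2.5-30 mL"; the interval between marks is not given.

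Section 15.1.1 has the milk scale checked monthly to within 1 gram. No check on ml readings is described. Section 2.2 lists intake as secondary and exploratory, whereas Section 2.3 names it as one of the hypotheses that determined power.

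**The concern.** Bib grams can be subtracted from milk grams directly. A weight per ml is needed only if the quantity being adjusted is in ml, so the text implies a volumetric gross intake. The documents name a scale for weights but no cylinder or syringe for volumes. The only graduated vessels described are the two study cups, so the natural reading is that ml come from the marks of the cup in use.

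In that case each arm of the comparison is measured with its own instrument. Coarser marks mean noisier readings. If the way of reading between marks also produces a systematic error, that error belongs to the cup. It appears whenever that cup is used, first or second, so the crossover cannot remove it and it is added to the estimated cup effect on intake. Only the analyst is blinded (Section 3.1); the research assistant who takes the readings can see which cup is in use.

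**Working it through.** **The plan's own figures.** The point rests on no stated figure. The nearest is the power statement in Section 2.3: 150 pairs, difference 5, SD 11, correlation 0.02 to 0.5, two-sided paired t-test, 90% power. With SD of the paired difference = 11 × √(2(1 − ρ)), this is 15.4 at ρ = 0.02 and 11.0 at ρ = 0.5. Power comes out at 97.7% and 99.98%, not 90%. The 80% quoted for carryover reproduces as 75 versus 75 in parallel (79.5%). The 90% mismatch is on the conservative side and is a separate matter. Only the SD, the correlations and n are used below.

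**Assumptions, not in the documents.** ml are read from the cup marks; medicine-cup marks every 2.5 ml; leftover volume uniform over the ranges shown; pre-feed volume either exact (20 ml) or uniform on 15 to 30 ml; the SD of 11 is in ml and applies to one value per cup.

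**Precision.** Reading to the nearest mark with step s gives an SD of s/√12 per reading and s/√6 for pre minus post.
- Nifty, s = 5: 5/√6 = 2.04 ml.
- Medicine cup, s = 2.5: 2.5/√6 = 1.02 ml.
- Paired difference at ρ = 0.02: √(15.40² + 25/6 + 6.25/6) = 15.57, against 15.40 without reading error. Power moves from 97.7% to 97.4%. As noise, the effect is negligible.

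**Mean shift, Nifty minus generic, with no true difference.** Reading down to a mark understates a volume spread over whole steps by s/2 on average: 2.5 ml (Nifty) and 1.25 ml (medicine cup). Simulation of the reading rules gives:

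| Reading rule | Leftover 0–2.5 ml | Leftover 0–5 or 0–10 ml |
|---|---|---|
| Nearest mark | +1.25 | 0 |
| Pre-feed exact, leftover read down | 0 | +1.25 |
| Pre-feed and leftover both read down | −1.25 | 0 |

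For example, with both readings taken down and leftovers under 2.5 ml, the Nifty error is −2.5 + 1.25 = −1.25 ml and the medicine-cup error is −1.25 + 1.25 = 0.

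**Consequence of a 1.25 ml shift at n = 150.**
- ρ = 0.02: SE = 15.4/√150 = 1.257; noncentrality 1.25/1.257 = 0.99; two-sided rejection probability 16.7%.
- ρ = 0.5: SE = 11/√150 = 0.898; noncentrality 1.25/0.898 = 1.39; rejection probability 28.2%.

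The nominal level is 5%. A shift of −1.25 ml gives the same rates in the other direction.

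**The conversion step alone.** If 20 ml weighing 20 g (taking 1 g per ml for illustration) is read as 22.5 ml, a 2-g spill converts to 2 × 22.5/20 = 2.25 ml, an error of 0.25 ml. This route is minor.

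**With weights.** Pre minus post minus bib gain, all in grams, uses no marks and no conversion. The reading terms above become zero, leaving only scale error, under the same procedure for both cups.

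**The case against.** The strongest objection is that the premise is inferred. Section 5.2.2 never says that ml are read from the feeding cup or that gross intake is volumetric; both units are recorded, and a weight per ml could equally serve to report a weighed intake in ml. This stands as a limit on the claim. It does not remove the gap: the sentence attaches the conversion to the subtraction of spillage, and the formula leaves the unit open.

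A reader might go further and infer that the error favours the Nifty, because leftovers below the lowest mark would count as swallowed and that band is wider in the Nifty (5 against 2.5 ml). If such leftovers are recorded as zero, the mean overstatement is m²/(2U) for lowest mark m and leftover uniform on 0 to U. With U = 5 this is 2.5 against 0.625 ml, a spurious gain of about 1.9 ml. The documents do not support that conclusion. It needs leftovers below the lowest mark set to zero while every other reading, including the pre-feed one, is exact, and no reading rule is stated. Other rules give no shift or the opposite sign. Nor does the text say that the weight per ml is recalculated at each feed.

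Two further objections hold in part. The medicine-cup marks come from a general description without a step size, so the contrast in precision is likely but not established. And a shift of 1.25 ml is small beside the 6.3 to 7.8 ml differences cited in Section 2.3: about a fifth or less (1.25/6.3 = 20%; 1.25/7.8 = 16%).

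**Conclusion.** The point holds as an ambiguity in the outcome definition with a possible, unsigned measurement error, not as a demonstrated bias. The text implies a ml-based intake, the two cups are marked differently, and a reading error tied to a cup would survive the crossover. Under the rules examined the shift is about 0, +1.25 or −1.25 ml. At 1.25 ml the error rate for intake would be about 17% to 28% in place of 5%, provided that ml are read from the marks, the medicine cup has 2.5-ml steps, and the SD of 11 is in ml.

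The reach is limited. The primary spillage outcome does not involve ml, and no sample size changes. Intake is exploratory in Section 2.2; its place in the Section 2.3 power statement gives it more weight than that label suggests. The change is best regarded as a free improvement: the plan already forms gross intake in grams as the denominator of percent spillage, and appears to use a less precise version of the same quantity for hypothesis 3.

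**What to change.** In Section 5.2.2, define intake per feed identically for both cups, in grams: pre-feed milk weight, plus the net weight added at each refill, minus post-feed milk weight, minus bib weight gain. Cup mass cancels in the difference if the same cup is weighed throughout; otherwise use weights net of the cup. Replace the sentence on weight per ml. If ml are wanted for reporting, convert with one fixed, stated density for both cups. Keep the ml readings only as a data-entry check against the weights.

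The cost is one paragraph of wording. Every weight needed is already to be recorded on the Feeding Assessment form, so there is no new data collection and no added staff time.

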2.2 Aim and Hypotheses

We aim to compare the Nifty Feeding Cup to a standardized, generic cup in up to 200 caregivers and their preterm infants. We will test the hypotheses that Nifty Feeding Cup feeding compared to generic cup feeding will result in:

Primary:

1. Less spillage.
2. Greater caregiver satisfaction

Secondary:

3. Greater intake of milk (accounting for spillage, exploratory)
4. Shorter feeds (exploratory)
5. Greater caregiver satisfaction 4 weeks post-discharge

Our aim and hypotheses were selected based on the most informative outcomes given the scope of the funding. The above hypotheses are framed in terms of the statistical alternative which is typically more intuitive to non-statisticians.

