2.3 Statistical Justification

Power for this study was determined by our primary hypotheses for the study H_A 1 related to amount of spillage and H_A 2 related to intake of milk. With 150 (up to 200) pairs, we estimate we will be able to detect at least a 5% difference in spillage or intake with 90% power and an alpha of 0.05 if no design effects are present. Carryover effects occur when a participant learns from cup feeding with the first cup which then affects the outcomes when feeding with the second cup. We will be able to statistically evaluate if carryover effects are present. If carryover effects are observed, we will have 80% power to detect an average 5% difference in spillage or intake.

These estimates are based on studies report differences in intake and spillage.⁸⁻¹⁰ We used the ‘power’ command in Stata 13.0 to estimate power using a two-sided paired t-test. We selected a conservative difference based on other studies, which showed differences between 6.3 and 7.8ml.⁸⁻¹⁰ We used a published estimate of a cup feeding standard deviation of 11¹⁰ and conservative correlations ranging from 0.02 to 0.5. This power calculation is also applicable to a 5% difference caregiver satisfaction between the two cups.

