3.1 Statistical Analysis

The data analyst will be blinded to the cup assignment. We will use generalized estimating equations for a crossover design to assess intake, spillage, and feeding duration and a sign test to assess the caregiver’s preference. Covariates may include factors such as amount of prior feeding, type of nutrition, number of prior cup feeds with assigned cup, and number of cup feeds between measured feedings. Most covariates typically accounted for (maternal age, other demographics) will not be included because the comparison is the same caregiver/infant pair.

We will conduct exploratory analyses stratifying on age (0-14 days and 15-28 days) and gestational age (<34 weeks and 34-36 weeks) to evaluate potential effect modification by these factors. These are exploratory since this study was not powered to detect effect modification. For each cup separately, we will compare estimates for those assigned the cup first to estimates for those assigned the cup second to evaluate for design effects. If design effects are observed we will analyze our data comparing those first assigned the Nifty cup to those first assigned to the medicine cup, dropping the data from the second cup and removing the cross over design from our study. We will use Stata 13.0 for all statistical analysis. Consistent with our power calculations, a two-sided p-value of 0.05 will be used.

A strength of our statistical approach is that participants with outcome data for at least one feeding assessment are able to be included in our GEE analyses even if other time points are missing. We will evaluate the potential effect of other missing data on our associations using multiple imputation methods.¹²

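### The satisfaction rating tagged primary has no planned test, Sections 2.2 and 2.3 disagree on hypothesis 2, and the power claimed for satisfaction uses no satisfaction input

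*Combined protocol and SAP*

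**What the plan says.** **Hypotheses.** Section 2.2 lists two primary hypotheses. The first is less spillage and the second is "2. Greater caregiver satisfaction". Its secondary list begins with "3. Greater intake of milk (accounting for spillage, exploratory"). Section 2.3 says that power was set by the primary hypotheses, and there the second of them is H_A "2 related to intake of milk".

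**Measures.** In Section 5.2.2 one sentence presents two items as the primary measure of satisfaction and then ranks them: "satisfaction will be the cup she prefers [secondary] and rated satisfaction [primary"]. Both come from the In-Hospital Preference Survey at Visit 5, after both cups have been used. The same section says that satisfaction with each cup is also recorded at each observed feed (Visits 2 to 5).

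**Analysis.** Section 3.1 assigns generalized estimating equations (GEE) to intake, spillage, "feeding duration and a sign test to assess the" caregiver's preference. Rated satisfaction does not appear. If design effects are seen, the first-assigned cups are compared between groups, "dropping the data from the second cup and removing the cross over design from our study". The significance level is a two-sided 0.05, with no rule for combining the two primaries.

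**Power.** Section 2.3 used Stata "to estimate power using a two-sided paired t-test", with a cup-feeding SD of 11, correlations of 0.02 to 0.5, and earlier studies reporting differences of 6.3 to 7.8 ml. It then adds: "This power calculation is also applicable to a 5% difference caregiver satisfaction between the two cups".

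**The concern.** Three gaps meet on one primary hypothesis. The sections disagree on whether hypothesis 2 is satisfaction or intake. The satisfaction measure tagged primary has no stated method, and the only satisfaction-type test belongs to the measure tagged secondary. The power quoted for satisfaction is borrowed from a feeding outcome.

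The analysis of a primary hypothesis could therefore be settled after the data are seen, and a reader cannot rely on the 90% (or 80%) for satisfaction. The design-effect fallback is also not spelled out for satisfaction. Nor does the plan say whether a positive conclusion needs one primary to succeed or both.

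**Working it through.** **1. Sections side by side**

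| Item | 2.2 | 2.3 | 5.2.2 | 3.1 |
|---|---|---|---|---|
| Spillage | primary, no. 1 | H_A 1, primary | outcome | GEE |
| Intake | secondary, exploratory, no. 3 | H_A 2, primary | outcome | GEE |
| Satisfaction: V5 rating | primary, no. 2 (satisfaction in general) | power said to carry over | tagged primary | no method |
| Satisfaction: cup preferred | primary, no. 2 (satisfaction in general) | power said to carry over | tagged secondary | sign test |

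The paired t-test appears in Section 2.3 only as a power method; it is not stated as the analysis of the rating.

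**2. The plan's own power figures**

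Inputs from Section 2.3: 150 pairs, SD 11, correlation ρ from 0.02 to 0.5, two-sided 0.05. Assumption: 5% is 5 units on the SD-11 scale, since no conversion is given.

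- SD of the within-pair difference = 11 × √(2(1 − ρ)), which is 15.4 at ρ = 0.02 and 11.0 at ρ = 0.5.
- Noncentrality = 5 × √150 / SD of difference, which is 3.98 and 5.57.
- Paired-t power (noncentral t, 149 df) is 97.7% and 99.98%. The plan states 90%.
- First-cup fallback, 75 v 75: noncentrality = 5 / (11 × √(2/75)) = 2.78, power 79.0%. The plan states 80%.

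This reading reproduces the fallback figure but not the main one, which it exceeds. The meaning of 5% is therefore not settled even for spillage and intake, and no input here comes from satisfaction.

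**3. How far satisfaction power depends on the missing inputs (illustration only)**

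Paired t, 150 pairs, 5-unit difference. The SDs other than 11 are assumptions.

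| Rating SD | ρ = 0.02 | ρ = 0.5 |
|---|---|---|
| 11 | 97.7% | 99.98% |
| 15 | 82.6% | 98.2% |
| 20 | 58.4% | 86.0% |

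Power is at least 90% only up to an SD of about 13.4 (ρ = 0.02) or 18.8 (ρ = 0.5).

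For the sign test on preference (secondary), 150 pairs without ties, the exact two-sided test rejects when 88 or more favour one cup (size 0.041). If 5% means a 55/45 split, power is 20.7%. If instead the standardised feeding effect carried over with normal differences (5/15.4 = 0.325 to 5/11 = 0.455), the share favouring one cup would be Φ(0.325) = 62.7% to Φ(0.455) = 67.5%, and power 86.7% to 99.1%. The answer turns on what 5% means.

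**4. The fallback**

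- Preference is a single choice between the cups, so it has no first-cup version.
- The V5 rating of Cup 1 could be compared between sequence groups, but it is given after exposure to both cups.
- Cup 1 ratings at Visits 2 and 3 are given before Cup 2 is handed over, so they allow a clean first-period comparison.

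**5. Two primaries at 0.05**

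If either alone supports a positive claim, family-wise error is 1 − 0.95² = 9.75% for independent tests and at most 0.05 + 0.05 = 10% in any case. If both must succeed, it is not inflated.

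**The case against.** Several counter-arguments have force.

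- **The tags already identify the primary measure.** They do, so naming it is a wording clean-up. They do not supply a test.
- **The analyst is blinded to cup assignment (Section 3.1).** This limits choosing a test to favour one cup. It does not stop a choice made by p-value.
- **The rating scale may be in the survey forms, which are separate attachments.** Its absence from this text is not counted as an error, and the SD grid above is hypothetical for that reason. A scale alone would still not provide a test, reconcile Sections 2.2 and 2.3, or turn a feeding SD into a satisfaction SD.
- **The lowest power figure concerns preference, the secondary measure.** That is correct, and it should not be quoted against the rating.

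A reader might infer three stronger conclusions that the documents do not support. One is that the trial is underpowered for satisfaction; a rating SD up to about 13 to 19 units would keep 90% power for a 5-unit difference. Another is that satisfaction has no usable analysis under the fallback; the Visit 2 and 3 ratings provide one. The third is that the type I error is necessarily inflated; that depends on a success rule the plan does not state.

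**Conclusion.** The point stands in limited form. That Sections 2.2 and 2.3 conflict on hypothesis 2, and that the rating tagged primary has no named analysis, follows from the text and needs no assumption. The satisfaction power is unsupported rather than shown to be low: between a rating SD of 11 and an assumed 20 it runs from 99.98% down to 58.4%, taking 5% as 5 units and ρ between 0.02 and 0.5. A fallback for satisfaction is available in the planned data but is not written down. The missing success rule matters only if one primary is enough for a positive claim, in which case the error rate is at most 10%. This should be corrected before the data are analysed.

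**What to change.** - **Section 2.3.** Remove the primary and H_A 2 labels from intake, and say that spillage and intake inputs set the sample size. Relabelling H_A 2 as satisfaction would be wrong, because satisfaction inputs did not determine it. Delete the sentence extending power to satisfaction, or replace it with power for the named test on the stated rating scale with an assumed SD.
- **Section 5.2.2.** State that the primary satisfaction measure is the within-pair difference in Visit 5 ratings (Nifty minus generic), with preference secondary.
- **Section 3.1.** Name the analysis of that difference, for example a Wilcoxon signed-rank test or the crossover GEE already planned, and keep the sign test for preference. State that, if the design-effect fallback is used, satisfaction is analysed by comparing Cup 1 ratings from Visits 2 and 3 between sequence groups.
- **Success rule.** State whether one or both primaries must succeed. If either suffices, name a multiplicity correction; the choice is the sponsor's.

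The cost is wording, with no new data. The stated satisfaction power may be withdrawn or become less favourable. The fallback comparison is weaker: for 5 units and 75 v 75, power is 52.7% at an assumed SD of 15 and 33.0% at 20.
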